Statistical Analysis	
The rates of all adverse events occurring within 24 hours post procedure, hospital discharge status and after discharge for all opened devices at each participating clinical site during the surveillance period will be summarized. The numbers of individual adverse events of each type and the per subject incidence rate for each type of adverse event will be determined and reported along with 90% two-sided exact binomial confidence intervals. Separate event counts and incidence rates with corresponding confidence intervals will be summarized for adverse events determined to be serious, device-related, serious and device-related, procedure-related, serious and procedure-related, and severe. Listings for all adverse events will be compiled that provide full descriptions of each adverse event including determination of the severity, seriousness, and relationship to the device or procedure. Discharge status will be described with counts and percentages.
 
Effectiveness at six months will be descriptively summarized in terms of the number and percentage of subjects achieving successful aneurysm occlusion measured by Raymond scale grade I and II and by clinical outcome as measured by mRS shift analysis comparing preprocedure mRS (up to 24 h prior to treatment) with 6 month mRS. In addition, tetrachotomized (0,1, 2, 3-6) mRS analysis will also be performed. mRS will also be evaluated at discharge and 30 days. Successful aneurysm occlusion will also be evaluated at the end of procedure. Stability of occlusion will be evaluated by comparing the two angiographic studies that are 6 months apart. The distribution of scores will be summarized by counts and percentages. If only three month Raymond scale value is available but not the six month, the three month value will be used in these analyses. Similarly, the last available earlier mRS values will be used if the six month value is not available.

-----------------------------	--

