### 3.1 Endpoints

#### Safety

- Periprocedural events\*: Rates of all adverse events occurring within 24 hours post-procedure and hospital discharge status.
- All adverse events at discharge and up to 30 days post procedure.
- Functional status at discharge and 30-days assessed using the modified Rankin Scale (mRS).

**Secondary safety endpoint:** evaluation of the extent of any relationship between adverse event rate to operator experience

(\* ) Including vessel perforation or dissection, intracranial aneurysm rupture, stroke, hemorrhage, death, inability to deploy or remove the device, and coil entanglement

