## 8. STATISTICAL ANALYSIS-

### 8.1 General Principles

The detailed hypothesis generation and statistical method is provided below:

The primary effectiveness endpoint is successful intracranial aneurysm occlusion (measured by Raymond Roy classification I or II) at the end of procedure, using digital subtraction angiography (DSA).

The performance goal (PG) for evaluating effectiveness is based on outcomes as reported in the Comaneci de novo, which was successful aneurysm occlusion of 79.7% (51/64). The PG for the primary effectiveness is defined as success rate cited above minus a margin of 10%, therefore giving a PG of 69.7%.

The resulting null and alternative statistical hypotheses are as follows:

H0:  $p \leq PG$

HA:  $p > PG$

The hypothesis test will be performed at an overall two-sided alpha level of 0.05 using Chi-square test, in which the lower confidence bound on the observed incidence of success is compared to the PG.

With a hypothesized true incidence rate of 82.6% for successful intracranial aneurysm occlusion at the end of procedure and desired power of  $\geq 80\%$ , using a normal approximation test with a nominal 0.025 one-sided significance level (equivalent to a two-sided alpha=0.05), the required evaluable sample size for primary efficacy is 90 evaluable patients with a power of 80%.

The objective of this postmarket surveillance study is to reduce uncertainty regarding the safety profile of the device and its real-world performance. This objective will be met by capturing safety data as the device is used in practice by physicians in the United States. As specified by FDA's order to conduct a postmarket surveillance study under section 522 of the Federal Food, Drug and Cosmetic Act (the act), 21 U.S.C. 360l, a total N=120 deployed devices with complete 30 day post procedure patient status. This number of deployments was later adjusted and approved by the FDA to 90 in the current version of the protocol (version 2.0) as explained above. The focus of the study is to characterize the incidence and nature of periprocedural events occurring within 24 hours post-procedure as well as hospital discharge status and to characterize 30-day post-procedure status including 30-day functional status and all adverse events after discharge to day 30 for each use of the Comaneci Embolization Assist Device. Longer terms effectiveness at six months will be also descriptively summarized in terms of the Raymond scale and mRS.

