## SUCCESS Study

has been broken, including whether consent was obtained or not, will be provided.

Accounting for all unsealed Comaneci devices in each IA case that may potentially require use of the Comaneci device at a clinical site for the period of enrollment to the study will be provided: for devices unsealed and not used in the SUCCESS intent to treat (ITT) group described below, the accounts will not provide patient information but will provide some indication of the device disposition. There will be a separate CRF to track the disposition of all devices for which the sterile seal has been broken, including whether the device was used in a subject in the ITT group.

Any patient who is consented for endovascular treatment of an intracranial aneurysm (IA) that may potentially require use of the Comaneci device at the participating centers in the study, and a Comaneci device's package sterile seal was broken will form the basis of ITT. ITT patients that Comaneci device was not introduced to the body will be considered screen failure, and will not be followed up, but the reason for not introducing the Comaneci will be documented.

The primary safety endpoint analysis will be performed using the ITT population without screen failures.

All patients who meet all of the inclusion criteria and no exclusion criteria will form the basis for FAS primary analysis- for whom primary safety and efficacy analysis will be performed.

Descriptive summaries of the peri-operative and post-operative adverse events in both the ITT cohort and the FAS cohort will be reported.

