## 8.2 Evaluation of Periprocedural Events

The rates of all adverse events occurring within 24 hours post procedure and hospital discharge status for all opened devices at each participating clinical site during the surveillance period will be summarized. Adverse events of special interest include vessel perforation or dissection, intracranial aneurysm rupture, stroke, hemorrhage, death, inability to deploy or remove the device, and coil entanglement. The numbers of individual adverse events of each type and the per subject incidence rate for each type of adverse event will be determined and reported along with 90% two-sided exact binomial confidence intervals. The upper bounds of 90% two-sided exact binomial confidence intervals are equivalent to the upper bounds of 95% one-sided exact binomial confidence intervals. While the estimated incidence rates for each type of adverse event will be taken as the most likely value of the true incidence rate, the corresponding upper bound of the one-sided 95% exact binomial confidence interval will be taken as the largest possible incidence rate consistent with the observed sample results.

Separate event counts and incidence rates with corresponding confidence intervals will be summarized for adverse events determined to be serious, device-related, serious and device-related, procedure-related, serious and procedure-related, and severe. Listings for all adverse events will be compiled that provide full descriptions of each adverse event including determination of the severity, seriousness, and relationship to the device or procedure. The following listings will be compiled:

- AE Listing 1 All AEs Sorted by Event Type
- AE Listing 2 All AEs Sorted by Subject and Relative Time of Onset
- AE Listing 3 Serious AEs
- AE Listing 4 Severe AEs
- AE Listing 5 Device-Related AEs
- AE Listing 6 Procedure-Related AEs
- AE Listing 7 Serious Device or Procedure Related AEs
- AE Listing 8 Severe Device or Procedure Related AEs

Discharge status will be described with counts and percentages.

Evaluation of the extent of any relationship between adverse event rate to operator experience will be evaluated. Operator experience will be evaluated by credentialing the investigators by years of training, number of aneurysms treated endovascularly in the last two years.

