### **8.3 30-day post-procedure status**

30-day functional status will be assessed using the modified Rankin Scale (mRS). This scale runs from 0-6, from no symptoms to death as follows:

- 0 - No symptoms
- 1 - No significant disability. Able to carry out all usual activities, despite some symptoms.
- 2 - Slight disability. Able to look after own affairs without assistance, but unable to carry out all previous activities.
- 3 - Moderate disability. Requires some help, but able to walk unassisted.
- 4 - Moderately severe disability. Unable to attend to own bodily needs without assistance, and unable to walk unassisted.
- 5 - Severe disability. Requires constant nursing care and attention, bedridden, incontinent.
- 6 - Dead.

The frequency distribution and cumulative frequency distribution of the 30-day mRS will be summarized using counts and percentages.

All adverse events after discharge (device-related and non device-related) for each use of the Comaneci Embolization Assist Device will be summarized similarly to how periprocedural events will be summarized as described above. This includes counts, per subject incidence rate, exact binomial confidence intervals, and a separate set of adverse event listings that contain full descriptions of each adverse event including determination of the severity, seriousness, and relationship to the device or procedure.

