### **8.6 Missing Data**

Since the primary safety endpoint is defined immediately post-procedure and up to 30 days, the amount of missing data for this study is anticipated to be low and so no imputation of missing data will be performed. For the analysis of six month effectiveness, if the six month Raymond score or mRS values are missing and any earlier data are available, the most recent earlier value will be used.

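### Windowed AE rates leave the time from 24 hours to discharge without a sure place in the 30-day safety endpoint, and the visit schedule conflicts with the discharge mRS endpoint

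*Combined protocol and SAP*

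**What the plan says.** **Adverse events.** Section 3.1 and the synopsis list two AE endpoints: rates within 24 hours (together with hospital discharge status), and "All adverse events at discharge and up to 30 days post procedure". Section 8.6 describes the period in one piece: "Since the primary safety endpoint is defined immediately post-procedure and up to 30 days". Section 8.1 plans an analysis of that endpoint: "The primary safety endpoint analysis will be performed using the ITT population without screen failures".

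The analysis sections then place the rates in time. Section 8.2 summarizes "The rates of all adverse events occurring within 24 hours post procedure and hospital discharge status for all opened devices", with 90% two-sided exact binomial intervals. Section 8.3 says "All adverse events after discharge (device-related and non device-related) for each use of the Comaneci Embolization Assist Device will be summarized similarly" to the periprocedural events, and 8.1 describes that later window as "all adverse events after discharge to day 30 for each use of the Comaneci Embolization Assist Device". The synopsis repeats the pair: "The rates of all adverse events occurring within 24 hours post procedure, hospital discharge status and after discharge for all opened devices". The second paragraph of 8.2 adds, with no time limit of its own, "Separate event counts and incidence rates with corresponding confidence intervals will be summarized for adverse events determined to be serious", and likewise for related and severe events.

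**Discharge mRS.** The synopsis and 3.1 make functional status at discharge, by mRS, a safety endpoint without exception. Section 7.4 asks for mRS at the 24-hour visit only where it happens to be done. Both schedules of events leave the 24-hour mRS cell empty. Section 7.5 does call for a discharge mRS, but applies only when discharge falls outside the 24-hour (-6/+12) window.

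**The concern.** Two windows, one ending at 24 hours and one starting at discharge, meet only if the subject leaves at 24 hours. The plan enrols ruptured aneurysms and provides a separate visit for later discharge, so longer stays are foreseen. What stands between the two windows in 8.2 and the synopsis is discharge status, which is a disposition reported by counts and percentages and not a period for counting events. Followed as written, the plan need not produce a per-subject rate covering the whole period that 8.6 calls primary. This matters because 8.2 takes the one-sided 95% upper bound as the largest incidence consistent with the data, and that bound is only as complete as the count behind it.

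The mRS question differs in kind. A site that follows the visit schedule exactly can leave a named endpoint unrecorded. The scores would be missing in a group defined by time of discharge, so the reported discharge distribution may not describe the cohort. Section 8.6 imputes nothing for safety, and a score not taken at discharge cannot be taken later.

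**Working it through.** **1. The plan's own figure.** The one computed design figure is N = 90 for the effectiveness test (8.1: performance goal 69.7%, assumed rate 82.6%, one-sided 0.025, 80% power).

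n = [(1.960·√(0.697·0.303) + 0.842·√(0.826·0.174)) / (0.826 − 0.697)]² = 89.4, rounded up to 90; power at 90 is 80.3%.

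It reproduces. The safety analyses have no computed figure, and nothing below changes this one.

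**2. The AE windows side by side.**

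| Source | Period |
|---|---|
| 8.6, primary safety endpoint | procedure to day 30 |
| 8.2 and synopsis, rate | 0 to 24 h |
| 8.3 and synopsis, rate | from discharge, no end stated |
| 8.1, same later window | discharge to day 30 |

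For discharge after 24 h, the interval from 24 h to discharge is in neither rate. For discharge before 24 h there is no gap; the windows overlap instead.

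**3. Where a gap event can still appear.** It is collected (7.5, 11.1) and listed (8.2). It may enter the post-operative summaries in 8.1, the category rates in the second paragraph of 8.2, the subgroup rates in 8.5 or the site analysis in 8.7. None of these states a window. A death also appears as grade 6 in the 30-day mRS table. The events least sure of any rate are those that are not serious, severe or related.

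**4. Size for AEs.** The documents give no lengths of stay or onset times, so the counts are assumptions. N = 90 is illustrative, because the size of the ITT population without screen failures is not stated. The upper bound of the 90% two-sided exact interval is the 0.95 quantile of Beta(x + 1, 90 − x).

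| Other subjects with the event | Gap-only subjects | Rate without gap (upper bound) | Rate with gap (upper bound) |
|---|---|---|---|
| 0 | 1 | 0% (3.3%) | 1.1% (5.2%) |
| 0 | 3 | 0% (3.3%) | 3.3% (8.4%) |
| 5 | 1 | 5.6% (11.3%) | 6.7% (12.7%) |
| 5 | 3 | 5.6% (11.3%) | 8.9% (15.5%) |
| 5 | 5 | 5.6% (11.3%) | 11.1% (18.1%) |

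Each gap-only subject adds 1/90 = 1.1 points. Split the five others as 3 within 24 h and 2 only after discharge: the planned windows show 3/90 = 3.3% and 2/90 = 2.2% whether there are no gap-only subjects or five, while the rate to day 30 moves from 5.6% to 11.1%.

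**5. The mRS visits.** The 24-hour window is 24 − 6 = 18 h to 24 + 12 = 36 h.

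| Discharge | Section that applies | mRS |
|---|---|---|
| before 18 h | 7.5 | called for |
| 18 to 36 h | 7.4 | only where done |
| after 36 h | 7.5 | called for |

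**6. Size for mRS.** If m of 90 subjects have no discharge score and c of 90 are observed in a category, the true share lies between c/90 and (c + m)/90, a width of m/90: 1.1 points for m = 1, 5.6 for m = 5, 10 for m = 9 and 20 for m = 18. Scores taken optionally under 7.4 reduce m.

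**The case against.** The strongest reply is that little is actually lost. Gap events are collected, listed and dated. A serious one can enter the untimed rates in 8.2, and a death is counted in the 30-day mRS. Section 3.1 itself separates the first 24 hours from discharge to day 30, so it may be read as the same split that section 8 uses; only 8.6, in a remark about missing data, states one continuous period. On mRS, the synopsis and 3.1 call for the score at discharge without exception, and 7.4 allows it, so the number missing could be zero. Safety is descriptive, and no test or sample size depends on either half.

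Most of this stands, and it limits the point. A reader might infer that an in-hospital stroke or death on day 3 would go uncounted; the listings, the untimed rates for serious events and the mRS table do not support that. A reader might also infer that events from day 30 to day 180 are left out of every summary. The text of 8.3 has no end date, while its heading and 8.1 point to day 30, so the limit is unclear rather than the events clearly omitted.

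What the reply does not answer is that possible inclusion in an untimed summary is not a specified rate for the endpoint. Nor does calling for discharge mRS in the endpoint list make the visit schedule collect it.

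**Conclusion.** The point holds in two limited parts.

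First, no windowed AE rate is sure to include events between 24 hours and discharge, and no cumulative rate to day 30 is specified for the period that 8.6 calls primary. Because onset is recorded, wording can repair this.

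Second, the endpoint list and the visit schedule conflict on discharge mRS for subjects leaving at 18 to 36 hours. This is an internal inconsistency. It would be too strong to say that the plan nowhere requires the score. It is nevertheless the more pressing half, because the loss is tied to discharge time and is permanent. Only the discharge time point is affected: pre-procedure and 30-day mRS are scheduled for everyone.

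The size cannot be derived from the documents and may be nil. The 1.1 points per subject, in either half, rests on an illustrative N of 90 and assumed counts. Both parts should be corrected; neither bears on the effectiveness test.

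**What to change.** **AE rates (8.1 to 8.3 and synopsis).** Add a cumulative per-subject AE rate from procedure to day 30, with the same 90% exact interval, as the analysis of the stated primary safety endpoint. Counting each subject once per event type also removes the overlap for discharge before 24 hours. A separate window from 24 hours to discharge is optional. State whether the 8.3 window ends at day 30 or day 180; if day 30, say where later events are summarized.

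**Discharge mRS (7.4, 7.5 and both schedules of events).** Reconcile these with the endpoint: record mRS at the 24-hour visit when that visit is also discharge, and use it as the discharge mRS. Report how many subjects have no discharge mRS.

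**Cost.** The AE change is wording only, since onset dates are already captured; the reported rate may be higher. The mRS change is one short assessment, by the independent clinician already in the plan, at a visit already taking place. It cannot recover scores for subjects already discharged without one. N = 90 and the effectiveness test are unchanged.

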### **8.5 Subgroup Analysis**

Selected adverse event rates will be provided for subgroups including wide-necked ruptured versus unruptured intracranial aneurysms.

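### The later adverse-event rate runs from each subject's own discharge to day 30, so it is not a 30-day risk, and section 8 plans no explicit fixed-window rate to day 30

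*Combined protocol and SAP*

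**What the plan says.** Section 8 plans two windowed adverse-event summaries.

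- **Periprocedural (8.2):** "The rates of all adverse events occurring within 24 hours post procedure and hospital discharge status for all opened devices", with per-subject incidence for each event type "reported along with 90% two-sided exact binomial confidence intervals". The same section takes the upper bound as the largest incidence compatible with the data.
- **After discharge (8.3):** "All adverse events after discharge (device-related and non device-related) for each use of the Comaneci Embolization Assist Device will be summarized similarly" to the first set. "This includes counts, per subject incidence rate, exact binomial confidence intervals" are specified, plus listings. Section 8.1 gives the window: "all adverse events after discharge to day 30 for each use of the Comaneci Embolization Assist Device".

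Section 8.3 states no denominator for the second rate. The synopsis ties both summaries to all opened devices, and section 8.1 says: "The primary safety endpoint analysis will be performed using the ITT population without screen failures". Neither text restricts the later rate to subjects discharged alive. Section 8.6 plans no imputation for safety and has no rule for in-hospital death or a stay beyond day 30.

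The endpoint in section 3.1 is worded more broadly: "All adverse events at discharge and up to 30 days post procedure". Section 8.5 adds: "Selected adverse event rates will be provided for subgroups including wide-necked ruptured versus unruptured intracranial aneurysms". It does not say which rates are selected.

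**The concern.** A post-discharge event can occur only between a subject's own discharge and day 30. A subject discharged on day 2 has 28 days in which to have one, a subject discharged on day 18 has 12, and a subject who never leaves hospital by day 30 has none. A per-subject proportion gives all three the same weight.

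This matters because the figure is likely to be read as the 30-day rate. Section 8.3 is headed as 30-day status, and the section 3.1 endpoint runs to 30 days after the procedure. Yet section 8 contains no explicit rate over that fixed period. Events between 24 hours and discharge are collected (sections 7.5 and 11.1), but neither 8.2 nor 8.3 clearly assigns them a rate. The in-hospital days missing from the later rate are therefore not clearly recovered elsewhere.

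If subjects with ruptured aneurysms, or with an early complication, stay longer, time at risk becomes tied to the subgroup or to the outcome. The documents do not report stays, so this is a plausible mechanism and not a documented fact.

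**Working it through.** **The plan's own figure.** No adverse-event rate is stated or assumed in the plan. The only computed figure is N = 90 for occlusion (8.1): [(1.96 × √(0.697 × 0.303) + 0.842 × √(0.826 × 0.174)) / (0.826 − 0.697)]² = 89.4, rounded up to 90, with power 80.3% at 90. It reproduces, and this point does not touch it.

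**Direction, with no assumptions.** Take all treated subjects as the denominator. Subjects with an event after discharge and by day 30 are a subset of those with an event between procedure and day 30. The first proportion therefore cannot exceed the second. With the denominator fixed, the exact upper bound rises with the count, so it cannot exceed its counterpart either.

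**Illustrative size.** The inputs below are assumptions, because the documents give none of them:

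- R = risk over 30 days at a constant daily hazard that is the same in both groups, so h = −ln(1 − R)/30. For R = 20%, h = 0.00744.
- Unruptured subjects are discharged on day 2, with no in-hospital deaths.
- Ruptured subjects are discharged on day L, and a share d die in hospital.
- Planned metric on all treated subjects = (1 − d) × (1 − exp(−h × (30 − L))).

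Unruptured, R = 20%: 1 − exp(−0.00744 × 28) = 18.8%.

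| Ruptured: L, d | Planned rate | Ratio to unruptured | Pooled rate, 40% ruptured |
|---|---|---|---|
| day 7, 0% | 15.7% | 0.84 | 17.6% |
| day 14, 10% | 10.1% | 0.54 | 15.3% |
| day 21, 20% | 5.2% | 0.28 | 13.4% |

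The daily hazards are equal, so the ratio would be 1 with equal time at risk. Over the same scenarios the ratio runs from 0.83 to 0.27 at R = 10% and from 0.84 to 0.29 at R = 30%. A separate set of assumptions gives a similar range. With h = 0.10/28 per day, the unruptured rate is 9.5%. The ruptured rate is 6.5% (day 10, 5% deaths) down to 2.7% (day 21, 15% deaths), ratios 0.69 to 0.28.

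**How much is the denominator alone?** Restricting to subjects discharged alive, at R = 20%, gives 11.2% for day 14 (ratio 0.60) and 6.5% for day 21 (ratio 0.34). Most of the shortfall remains, because the window is still shorter. As a pure denominator effect, suppose 9 subjects have events and 9 of 90 are never discharged by day 30:

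- 9/90 = 10.0% (90% CI 5.3% to 16.8%)
- 9/81 = 11.1% (90% CI 5.9% to 18.6%)

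**Fixed window.** Without in-hospital deaths, counting from the procedure gives 20% in both groups by construction. In-hospital deaths would be counted as events and would raise the group in which they occur.

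**The case against.** The strongest reply is that nothing is biased. As the proportion of subjects with an event after discharge, the planned figure estimates exactly what it names. No hypothesis, performance goal or threshold rests on it, and the safety aim is descriptive. That stands: the fault lies in reading or comparing it as a 30-day rate.

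A reader might also infer that the plan counts in-hospital deaths and long stays in full. The documents do not state this. It is inferred from the synopsis wording on opened devices and from the safety population in 8.1. The supportable statement is that the denominator is unspecified and that nothing removes those subjects.

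A reader might further infer that the ruptured versus unruptured comparison is distorted. Section 8.5 does not name this rate and plans no test, and the selected rates could be the 24-hour ones, which have a fixed window. The distortion is conditional.

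There is some mitigation. The section 3.1 endpoint can be read as anchored on the procedure. The 30-day mRS table shows deaths as category 6. Section 8.7 summarises any serious or device-related event by site without a discharge-based start. Listings give events by time of onset. None of these is an explicit overall incidence from procedure to day 30.

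**Conclusion.** The point holds in a limited form. The post-discharge proportion is valid as a description of what happens after discharge, but it does not estimate 30-day risk. Followed as written, section 8 gives no explicit fixed-window rate that does, although the section 3.1 endpoint extends to day 30. Taken as the 30-day rate on all treated subjects, the proportion and its upper bound are too low or unchanged; that direction needs no assumption.

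The size is unknown. The illustrative ratio of about 0.8 to 0.3 rests wholly on assumed stays, assumed in-hospital mortality and equal constant hazards, and it shows only that the mechanism could be material. The documents do not support a claim that the planned estimator is itself biased or that the subgroup summary will be misleading. The point is worth acting on because the missing summary is cheap to add.

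**What to change.** 1. Add to section 8.3 and the synopsis, as the main 30-day safety summary, the per-subject incidence from procedure to day 30 by date of onset, with the exact binomial interval already planned. Include in-hospital events and deaths, cover all treated subjects, and report it overall and by rupture status. Show 24 hours to day 30 separately.
2. Name this fixed-window rate in section 8.5 as the one used for ruptured versus unruptured.
3. Keep the post-discharge summary as secondary and state its denominator as subjects discharged alive before day 30. Events per person-day are optional.
4. Reconcile the synopsis with sections 3.1, 8.1, 8.2 and 8.3 so that the windows match the endpoint.

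The cost is analysis wording and one more table, with no new visits. Treatment date (7.2.1) and event onset (11.1) are already collected. Section 7.5 does not list a discharge date explicitly, but the fixed window does not need one, and the existing post-discharge summary already requires discharge timing. One dependency should be confirmed: 11.1 starts event recording at consent, which may follow the procedure by up to 72 hours in ruptured cases, so the text should say that events from the procedure onward are captured for them. The downside is a 30-day figure that may look less favourable.
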